The choice of a primary endpoint in metastatic CRPC is difficult as this disease is characterized by a poor ability to measure response and PFS, the typical primary endpoints in phase II trials. Measurable lesions by RECIST are seldom observed, since the most common site of metastases is bone, a non-measurable site [26]. Although, a $\geq 30\%$ or $\geq 50\%$ PSA decline within 3 months and time to clinical progression may be useful surrogates for long-term outcomes with chemotherapeutic agents, its validity with biological agents is unknown [27-29]. Regression of measurable tumor was associated with survival in one study, but external validation is required and measurable tumors are found in the minority of patients. Prostate Cancer Working Group (PCWG)-2 guidelines recommend time to event primary endpoints rather than response endpoints [27]. Moreover, an early switch in therapy within 3 months was discouraged due to the poor reliability of early changes in PSA and bone scans. Vaccines may potentially induce a transient rise in PSA as well as increases in size of measurable lesions by provoking an immune reaction in the normal and malignant prostate tissue. Guidelines have been recommended to standardize methodology used for the calculation and employment of PSA doubling time changes to provide a signal of activity in early trials [30].

Changes in CTCs (circulating tumor cells) appear promising as prognostic factors in the setting of chemotherapy and abiraterone, but require validation in the context of biologic agents [31, 32]. Moreover, it is unclear if unfavorable CTC alterations can be utilized to switch therapy. CTC is emerging as a highly important prognostic marker for metastatic CRPC and appears better than PSA. In one prospective trial, blood was drawn from CRPC patients with progressive disease starting a new line of chemotherapy before

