In another study, CTC count was assessed as a prognostic factor for survival in patients with progressive, metastatic, castration-resistant prostate cancer receiving first-line chemotherapy.[33, 34] The investigators identified patients with progressive metastatic castration-resistant prostate cancer starting first-line chemotherapy in the IMMC38 trial. CTCs were isolated by immunomagnetic capture from blood samples at baseline and after treatment. Baseline variables, including CTC count, PSA, LDH, and post-treatment variables (change in CTCs and PSA) were tested for association with survival with Cox proportional hazards models. Concordance probability estimates were used to gauge discriminatory strength of the informative factors in identifying patients at low-risk and high-risk of survival. Variables associated with high risk of death were high LDH (hazard ratio 6.44), high CTC (HR 1.58), high PSA (HR 1.26), low albumin (HR 0.10), and low hemoglobin (HR 0.72) at baseline. At 4 weeks, 8 weeks, and 12 weeks after treatment, changes in CTC number were strongly associated with risk, whereas changes in PSA were weakly or not associated ($P > 0.04$). The most predictive factors for survival were LDH concentration and CTC counts. Thus, CTC number, analyzed as a continuous variable was useful to monitor disease status as an intermediate endpoint of survival in clinical trials. Prospective recording of CTCs as an intermediate endpoint in randomized clinical trials was felt to be warranted. Recently, the Phase III database of patients where abiraterone acetate was compared with placebo was investigated for prognostic factors. Baseline LDH and favorable CTC changes were independently significant. [32]

Therefore, overall survival is the only currently reliable endpoint for randomized phase III trials of in metastatic CRPC. Primary endpoints in phase II trials may need to be tailored based on mechanism of activity on agents. Generally, phase II trials evaluating new biologic agents are employing PFS based on clinical and radiographic endpoints in accordance with PCWG-2 guidelines, and not PSA-based changes. For example, the recent randomized phase II trial evaluating tasquinimod, a novel antiangiogenic and immune-modulating agent, employed these new guidelines and did not use PSA changes alone to make clinical decisions.[35]

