2.2 Secondary Objectives

- PSA changes (response, PSA decline $\geq 30\%$ within 3 months)
- CTC changes (unfavorable \rightarrow favorable, $>30\%$ decline)
- Measurable disease response rate (RECIST)
- Pain responses (decline in present pain index ≥ 2 , decrease in analgesics)
- Overall Survival

- Toxicities
- Association of outcomes with baseline whole blood 20S proteasome level

[figure not shown]

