Modest activity is considered clinically meaningful in this relatively heavily pretreated population with metastatic CRPC that has received abiraterone acetate and/or enzalutamide (prior chemotherapy and sipuleucel-T are allowed). The null hypothesis for this trial is that the primary endpoint of 6-month PFS <10% is not clinically meaningful and the alternative hypothesis is that the true clinical PFS of interest is $\geq 30\%$. Since we will follow all subjects for at least 6 months or until progression or death, we will not have censoring and 6 months PFS can be treated as a binomial random variable. With twenty five evaluable patients we will have 80% power for an exact binomial test at the one sided 0.05 significance level of the null hypothesis that the 6-month PFS rate is 10% if the actual rate is 30%. That null hypothesis will be rejected if 6 or more of the 25 subjects survive for 6 months progression free. Twenty-eight subjects will be accrued to allow for 10% inevaluable patients.

Sample Size/Accrual Rate

A total of 28 patients will be enrolled for this trial. Accrual period will be 6 to 12 months.

Analysis of Secondary Endpoints

The Kaplan-Meier method will be used to estimate PFS and OS rates over time with standard errors estimated using Greenwood's formula. Medians and their 95% confidence intervals will also be estimated. PSA response, PSA decline $\geq 30\%$ within 3 months, RECIST responses and regressions, pain response and CTC alterations will be analyzed as secondary endpoints. CTC changes will include changes from unfavorable ($\leq 5/7.5\text{ml}$) to favorable, and declines by $>30\%$. Pain response is defined as decline in present pain index ≥ 2 points and/or decrease in analgesics. Linear regression with PSA as the dependent variable and time as the dependent variable will be performed and used to estimate PSA DT. The association of baseline whole blood 20S proteasome level with PFS and other secondary endpoints will be examined using Cox regression to generate hypotheses for selecting suitable patients for further study.

Reporting and Exclusions

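### Section 10 ties only yes/no PSA and CTC outcomes to the 20S proteasome analysis; adding continuous change from data already collected would recover power that a 25-patient trial can ill spare

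*Combined protocol and SAP*

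**What the plan says.** Section 2.2 sets as a secondary objective "Association of outcomes with baseline whole blood 20S proteasome level". Section 10, under Analysis of Secondary Endpoints, names "PSA response, PSA decline $\geq 30\%$ within 3 months, RECIST responses and regressions, pain response and CTC alterations" as the secondary endpoints beside PFS and OS. It specifies the CTC changes as conversion from unfavorable to favorable and a decline of more than 30%. PSA response is not defined further, and I read it as a yes/no outcome. Baseline 20S level is then to be related to PFS and the other secondary endpoints by Cox regression, in order to generate hypotheses about which patients to study next.

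Two details limit how strongly this can be read. The same paragraph plans a linear regression of serial PSA on time to estimate PSA doubling time, which is a continuous summary. The sentence on CTC changes says what they will include, which does not exclude other summaries. Neither is linked to 20S.

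The underlying data are richer than the cuts. The study calendar has PSA at baseline and on day 1 of every cycle, and Section 12 has CTC counts at baseline and on day 1 of cycles 2 and 4.

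The only power statement in the plan concerns the primary endpoint: "With twenty five evaluable patients we will have 80% power for an exact binomial test at the one sided 0.05 significance level".

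**The concern.** A cut outcome treats a patient whose PSA falls by 31% like one whose PSA falls by 95%, and separates the first from a patient at 29%. With about 25 patients, discarding that ordering weakens any association with a continuous biomarker. The 20S analysis is meant to point to patients for further study, so the risk is that a real moderate association goes unseen although the data to show it were collected.

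The background section gives some support for the full scale. On a cited reanalysis of CTC data, Section 1.1 says that "CTC number, analyzed as a continuous variable was useful to monitor disease status as an intermediate endpoint". On PSA declines of 30% or 50% as surrogates, it says that "its validity with biological agents is unknown". The second remark concerns surrogacy and does not itself favour continuous PSA. It means only that the documents do not justify these particular thresholds for this agent. No reason is given for using cuts in the biomarker association, as opposed to reporting them as familiar rates.

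**Working it through.** **Step 1: the plan's own figure.** Inputs from Section 10: 25 evaluable patients, 10% against 30%, and the rule "That null hypothesis will be rejected if 6 or more of the 25 subjects survive for 6 months progression free". Exact binomial: P(X ≥ 6 | n = 25, p = 0.10) = 0.0334 and P(X ≥ 6 | n = 25, p = 0.30) = 0.8065. A threshold of 5 would give a type I error of 0.098. Accrual: 25 / (1 − 0.10) = 27.8, rounded up to 28. The stated design reproduces. It says nothing about the 20S analysis, for which no power is stated.

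**Step 2: assumptions for the 20S analysis.** The documents give no correlation, responder share or significance level, so these are mine. Baseline 20S level and log change are bivariate normal with correlation ρ; n = 25; two-sided 0.05. The full-scale test is Spearman; the test after the cut is a rank test of 20S level between responders and non-responders. As an anchor for the responder share, Section 1.1 cites a PSA decline of at least 50% in 26% of patients given docetaxel after abiraterone.

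**Step 3: simulated power (%).** Entries cover two runs, of 40,000 and 20,000 replicates.

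| ρ | Full scale | Cut, 50% responders | Cut, 30% | Cut, 15% |
|---|---|---|---|---|
| 0.3 | 28 | 20–21 | 18–19 | 13 |
| 0.4 | 47 | 33–34 | 30–31 | 21 |
| 0.5 | 68–69 | 50–52 | 45–46 | 32 |
| 0.6 | 87 | 69–71 | 64 | 45–46 |

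Losses, by subtraction within each run:
- 50% responders: from 28 − 21 = 7 to 68 − 50 = 18 points.
- 30% responders: from 28 − 19 = 9 to 69 − 46 = 23 points.
- 15% responders: from 28 − 13 = 15 to 87 − 45 = 42 points.

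At ρ = 0.2, power of about 15% falls to 11%, 10% and 8%, a loss of about 4 to 7 points. With no association, Spearman rejected in about 5% of runs and the binary rank test in about 3–5%. A continuity correction in the rank test moves entries by one to three points, so the ends of these ranges are approximate.

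**Step 4: hand check at ρ = 0.5.** Cutting a normal outcome at responder share p reduces the correlation to ρ·φ(z_p)/√(p(1 − p)). The Fisher z approximation gives power Φ(atanh(r)·√(n − 3) − 1.96), with √22 = 4.69.
- Full scale: 0.549 × 4.69 = 2.58, power about 73%.
- p = 0.50: r = 0.5 × 0.399/0.500 = 0.399; 0.422 × 4.69 = 1.98, power about 51%.
- p = 0.30: r = 0.5 × 0.348/0.458 = 0.379; 0.399 × 4.69 = 1.87, power about 47%.
- p = 0.15: r = 0.5 × 0.233/0.357 = 0.327; 0.339 × 4.69 = 1.59, power about 36%.

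This parametric version gives losses of about 22, 26 and 37 points, the same order as the rank tests.

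**Step 5: CTC conversion.** Only patients unfavorable at baseline can convert. Section 1.1 reports 57% in a cited cohort (5 or more cells per 7.5 mL); if that applied here, 0.57 × 25 ≈ 14 patients. At n = 14 and ρ = 0.5, full-scale power is about 41%, against 24–27% after a cut at 30–50% converting. Against about 69% for all 25, some 69 − 41 = 28 points come from the smaller subset and 14–17 points from the cut. These are different losses and should not be added together as the cost of cutting.

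Counts near zero also reduce the full-scale gain. In an illustrative simulation with Poisson counts, median about 6.5 and log-change SD 1 (all assumed), full-scale power at ρ = 0.5 with 25 patients was 45%, against 29% for the decline of more than 30%, a loss of 16 points.

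**The case against.** The strongest case on the other side has four parts.

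First, a reader might infer that the plan analyses PSA and CTC solely as cuts. It does not say so: PSA doubling time is planned, and the CTC list is not closed. This stands. The accurate statement is that no continuous PSA or CTC outcome is expressly tied to 20S.

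Second, a reader might take the power losses as a property of this trial. The documents do not support that. Correlation, responder share and significance level are all assumed, and the 42-point figure needs a correlation of 0.6 with 15% responders. At weak correlations the loss is a few points. The comparison also uses a rank test on a one-time cut, whereas the plan names Cox regression, whose use for outcomes that are not times to event is unclear. That is a separate matter: a suitable binary-outcome model would still lose the information that the cut discards.

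Third, the consequence is modest. The analysis is exploratory, has no rule for dropping the biomarker, and keeps PFS and OS as time-to-event outcomes. Even on the full scale, power is only 28–47% at correlations of 0.3–0.4. This stands and keeps the point minor.

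Fourth, cuts have merits. Section 1.1 reports that conversion to favorable CTC carried prognostic meaning (6.8 to 21.3 months). A responder endpoint can count early deaths and dropouts as failures, whereas a log change needs a post-baseline sample. This too stands, and it shapes the fix: the rates stay, and missing post-baseline values need a rule.

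**Conclusion.** The point holds as a low-cost improvement, not as an error. Section 10 names yes/no PSA and CTC outcomes for the 20S association and ties no continuous change to it, although the serial measurements are collected. Given the assumptions in the working, the loss at 25 patients is about 7–18 points with 50% responders, 9–23 with 30% and 15–42 with 15%, for correlations of 0.3 to 0.6. It is about 4–7 points at correlation 0.2, and probably smaller for CTC than the normal model suggests where counts are near zero. None of these figures can be derived from the documents. It would be wrong to conclude that any stated power figure fails or that the primary analysis is weakened: the exact test gives 0.0334 and 0.8065, as planned.

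**What to change.** In Section 10 and the matching Synopsis paragraph:
- Keep the PSA and CTC responder rates as secondary endpoints, each with a 95% confidence interval.
- For the 20S association, add two continuous outcomes: log(lowest PSA within 3 months / baseline PSA), and log((CTC + 1)/(baseline CTC + 1)) at cycles 2 and 4.
- Relate each to baseline 20S level by Spearman correlation, or by linear or mixed regression on log 20S adjusted for the baseline value of the marker, with 95% confidence intervals.
- In a sensitivity analysis, rank patients who die or progress before a post-baseline sample as having the worst outcome. Report how many patients lack samples.

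The cost is a few sentences of plan text and a little analysis code, with no new samples, visits or patients. There are three drawbacks. Log changes are less familiar to clinicians than responder rates. Early dropouts need explicit handling. The lowest PSA depends partly on how many visits a patient completed, so the number of PSA values per patient should be reported beside it.

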treatment and monthly thereafter.[31] Patients were stratified into predetermined Favorable or Unfavorable groups (<5 and ≥ 5 CTC/7.5mL). Two hundred thirty-one of 276 enrolled patients (84%) demonstrated CTCs and were evaluable. Patients with Unfavorable pretreatment CTC (57%) had shorter OS (median OS, 11.5 versus 21.7 months; Cox hazard ratio, 3.3; $P < 0.0001$). Unfavorable post-treatment CTC counts also predicted shorter OS at 2 to 5, 6 to 8, 9 to 12, and 13 to 20 weeks (median OS, 6.7-9.5 versus 19.6-20.7 months; Cox hazard ratio, 3.6-6.5; $P < 0.0001$). CTC counts predicted OS better than PSA decrement algorithms at all time points; area under the receiver operator curve for CTC was 81% to 87% and 58% to 68% for 30% PSA reduction ($P = 0.0218$). Prognosis for patients with (a) Unfavorable baseline CTC who converted to Favorable CTC improved (6.8 to 21.3 months); (b) Favorable baseline CTC who converted to Unfavorable worsened (>26 to 9.3 months). These data led to Food and Drug Administration clearance of this assay for the evaluation of CRPC.

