Pain response and progression

Patients with a PPI score of at least 2, or need for analgesics, or both at baseline are assessed for the pain response. A pain response is defined as a two-point reduction in the PPI score from baseline without an increase in the analgesic use or as a reduction in analgesic use without an increase in the PPI score. Pain progression is defined as an increase in the PPI score of at least one point from the nadir, an increase in analgesic use, or a requirement for palliative radiotherapy.

Progression-Free Survival

PFS is defined as the duration of time from start of treatment to time of progression or death, whichever comes first.

12. **CORRELATIVE STUDIES**

Circulating Tumor Cell (CTC) enumeration will be used as a secondary marker for efficacy of response to the treatment. Baseline CTC will be obtained prior to initiation of therapy and day 1 of cycles 2 and 4. Baseline whole blood 20S proteasome activity will also be determined.

CTC enumeration

The CELLSEARCH[®] System led to the first standardized, FDA-cleared semi-automated system that detects and enumerates CTCs of epithelial origin (CD45-, EpCAM+, and cytokeratins 8, 18+, and/or 19+) from a 7.5-mL blood sample with high sensitivity and specificity. The CELLSEARCH[®] System uses unique immunomagnetic and fluorescence imaging technology to provide rapid and reproducible analysis of CTCs with a simple 3-step process: sample collection, sample preparation, and sample analysis. System components include:

- Proprietary CellSave Preservative sample tubes
- CELLSEARCH[®] CTC Test and Control kits
- Automated CELLTRACKS[®] AUTOPREP[®] System
- CELLTRACKS ANALYZER II[®]

CellSave Preservative tubes provide an optimized cell preservative that stabilizes CTCs for up to 96 hours at room temperature, which allows shipment of samples to remote locations for analysis and improves the reproducibility and reliability of CTC analysis. CTCs are fragile and tend to degrade within a few hours when collected in standard evacuated blood collection tubes.

Once the blood sample is collected for UAB patients, the tube will be delivered to UAB main laboratory to be sent out to Quest Diagnostics for CTC enumeration. For outside sites, the tube will be sent directly to Quest Diagnostics for CTC enumeration.

Whole Blood 20S Proteasome Activity

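### As transcribed, Section 10's cutoff for unfavorable CTC runs opposite to Section 1.1, so the conversion endpoint read literally omits falls such as 20 to 3 (minor)

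*Combined protocol and SAP*

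**What the plan says.** Section 2.2 lists the CTC objective as "CTC changes (unfavorable \rightarrow favorable, $>30\%$ decline", without a cutoff. Section 12 sets the sampling times, "Baseline CTC will be obtained prior to initiation of therapy and day 1 of cycles 2 and 4", and describes the assay, again without a cutoff.

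The only number that the plan attaches to its own conversion endpoint is in Section 10, Analysis of Secondary Endpoints: "CTC changes will include changes from unfavorable ($\leq 5/7.5\text{ml}$) to favorable". The sentence goes on to name a decline of more than 30% as the other CTC change of interest. It gives no number for favorable.

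The only other cutoff is in Section 1.1, in the account of a cited prospective study: "Patients were stratified into predetermined Favorable or Unfavorable groups (<5 and" 5 or more per 7.5 mL, respectively. That account also gives the direction of prognosis. "Patients with Unfavorable pretreatment CTC (57%) had shorter OS", with medians of 11.5 against 21.7 months, and prognosis for patients with "Unfavorable baseline CTC who converted to Favorable CTC improved (6.8 to 21.3 months").

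The same Section 10 paragraph plans a linear regression to estimate PSA doubling time. It names both PSA and time as the dependent variable and mentions no log transform.

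**The concern.** Section 10 attaches the unfavorable label to low counts, whereas Section 1.1 attaches it to high counts and ties high counts to shorter survival. Section 10 also disagrees with itself: one half of the CTC sentence treats a falling count as the change of interest, and the other half, taken literally, does not.

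At stake is the conversion rate, a listed secondary objective. A literal analysis would leave out the change that Section 1.1 associates with better survival. An analyst who noticed the problem would have to depart from the written definition and choose a cutoff that Section 10 does not state, possibly after seeing the data.

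**Working it through.** The plan gives no figure to reproduce here. The check is to apply the definitions as classification rules.

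**Inputs.** Let b be the baseline count and f the follow-up count, per 7.5 mL.
- Section 1.1 rule: conversion if b ≥ 5 and f < 5.
- Section 10, reading A (favorable is the complement of unfavorable): conversion if b ≤ 5 and f > 5.
- Section 10, reading B (favorable borrowed from Section 1.1): conversion if b ≤ 5 and f < 5. Counts of 0 to 4 are then both unfavorable and favorable.
- Decline criterion (Sections 2.2 and 10): (b − f)/b > 0.30.

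**Example pairs.**

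| b to f | Section 1.1 | Reading A | Reading B | Decline >30% |
|---|---|---|---|---|
| 20 to 3 | yes | no | no | yes (17/20 = 85%) |
| 3 to 20 | no | yes | no | no |
| 3 to 3 | no | no | yes | no (0%) |
| 5 to 4 | yes | no | yes | no (1/5 = 20%) |

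**All integer pairs from 0 to 50.** This shows the logic of the rules. It is not a model of patients.
- Section 1.1: 46 baseline values (5 to 50) × 5 follow-up values (0 to 4) = 230 pairs, all falls.
- Reading A: 6 baseline values (0 to 5) × 45 follow-up values (6 to 50) = 270 pairs, all rises. None is shared with the 230.
- Reading B: 6 × 5 = 30 pairs, of which 15 are falls, 5 unchanged and 10 rises. Five are shared with the 230, all from a baseline of exactly 5.

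The direction is reversed, but the two definitions of unfavorable are not exact complements: a count of exactly 5 is unfavorable under both.

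**What the decline criterion recovers.** For b ≥ 6 and f ≤ 4, the smallest fall is 6 to 4, or 2/6 = 33%, which exceeds 30%. For b = 5, the fall to 3 is 40% and the fall to 4 is 20%. So 229 of the 230 Section 1.1 conversions also meet >30% decline, and the only exception is 5 to 4. This holds for any upper limit on the count.

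**PSA doubling time.** On a straight line PSA = a + bt (here b is the slope), the time needed to double from time t is (a + bt)/b = a/b + t. It changes with the starting point, so the line has no single doubling time. On ln(PSA) = a + bt, the doubling time is ln2/b at every t.

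**The case against.** The strongest objection is that the point rests on one inequality sign in text extracted from a PDF. The extraction may contain misreads elsewhere: one reference appears in both reference lists with its lead author's surname spelled differently. The paragraph does show the opposite sign where it is expected, for example "Pain response is defined as decline in present pain index ≥ 2 points and/or decrease in analgesics", but that does not prove that this instance is right. This objection stands. It limits confidence to medium and makes checking the PDF the first step. If the PDF shows the opposite sign, the contradiction disappears and only the unstated favorable cutoff remains.

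A second objection is that the intended direction is clear. The labels are explained only in Section 1.1, conversion is paired with decline wherever it is listed, and Section 12 uses CTC as an efficacy marker. This stands in large part. A reader might infer from the literal text that the trial will report rising CTC counts as success. The documents do not support that: it follows only under reading A and contradicts the stated purpose of the marker. What remains is that Section 10 is where the analyst looks for the definition, and the definition there is wrong as transcribed.

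Third, PSA doubling time is not a listed secondary objective, and calling time dependent is plainly a slip. Section 1.1 mentions guidelines on calculating doubling time, but Section 10 does not invoke them. The missing log transform is therefore worth one corrected sentence and adds nothing to the severity.

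**Conclusion.** The point holds as a minor correction. As transcribed, Section 10 defines unfavorable CTC in the direction opposite to Section 1.1 and inconsistently with its own decline criterion. Applied literally, it omits conversions such as 20 to 3. If favorable means above 5, it counts only rises.

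The effect is confined to one component of one secondary endpoint, and nearly all the omitted falls still count under >30% decline. A reader might infer that the trial's main conclusion is at risk. It is not: the primary endpoint is clinical PFS at 6 months, and neither the sample size (25 evaluable, 28 enrolled) nor the 6-of-25 rule uses CTC data.

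A reader might also take the 57% unfavorable at baseline in the cited study as a guide to how many men here would be misclassified. It cannot serve that purpose. It describes men starting a new line of chemotherapy, and being unfavorable at baseline is not the same as converting.

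The conclusion assumes that the symbol is transcribed correctly and that the trial intends the same labels as Section 1.1, since the documents offer no other meaning for them.

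**What to change.** 1. Check the inequality sign in Section 10 against the source PDF. If it is as transcribed, state that unfavorable is ≥5/7.5 mL and favorable is <5/7.5 mL. If the PDF shows the opposite sign, add only the favorable cutoff.
2. Report conversion among all eligible patients who are unfavorable at baseline, and count those without a follow-up CTC as non-converters. Reporting and Exclusions in Section 10 bases conclusions on all eligible patients and, for the response rate, treats early death and unknown status as failure. That rule is not written for CTC, but the same principle applies. A denominator limited to men with a follow-up count would drop those who die or leave before cycle 2 or 4 and could inflate the rate, so it should be a sensitivity figure at most.
3. In the same paragraph, make ln(PSA) the dependent variable and time the independent variable, with PSA doubling time = ln2/slope.

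The cost is one symbol, one added cutoff, and a sentence each for the denominator and the PSA regression. No new data, visits or patients are needed.

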6.3 Duration of Therapy

Therapy will continue until progression (as defined below) or severe toxicities. Acyclovir will continue from day 1 of cycle 1 until ≥7 days after the last dose of carfilzomib. Androgen deprivation therapy with LHRH analogue or antagonist and bone protecting agent (denosumab or zoledronic acid) will also continue. If the bone protective agent has not already been initiated ≥4 weeks before trial registration, initiation of a bone protection agent is not allowed. CMP evaluations are performed on day 1 every 4 weeks,

CBC on days 1, 8 and 15 every cycle, and radiological evaluations are performed every 3 cycles or earlier if clinically indicated. Correlative studies include serial CTC enumeration (repeated on day 1 cycle 2, then q 3 cycles) and collection of whole blood is performed at baseline for 20S proteasome activity and other potential future correlative studies.

Progression of disease will be defined clinically as the first occurrence of any of the following and PSA progression alone will not constitute progression.

- 1) Two distinct new lesions on bone scan consistent with bone metastases in the best judgment of the investigator and confirmed by further new lesions on a subsequent scan ≥ 6 weeks later.
- 2) Progression in measurable disease as defined by RECIST criteria
- 3) Worsening of pain in the judgment of the investigator.
- 4) New bladder outlet or ureteral obstruction caused by cancer
- 5) New bone related events
 - a. Pathologic fracture
 - b. Spinal cord compression
 - c. Need for palliative radiation, surgery, or kyphoplasty to any neoplastic bone lesion
- 6) Deterioration of performance status to ECOG level 3-4
- 7) Death

Therapy is also discontinued for other non-progression events below:

- 1) Intercurrent illness that prevents further administration of treatment
- 2) Unacceptable adverse event(s)
- 3) Patient decides to withdraw from the study
- 4) General or specific changes in the patient's condition render the patient unacceptable for further treatment in the judgment of the investigator.

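### The CTC decline criterion (more than 30%) has no baseline floor, so a patient who starts with one to four cells counts as a responder after losing one or two

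*Combined protocol and SAP*

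**What the plan says.** The synopsis and Section 2.2 list two CTC outcomes: conversion, which begins "CTC changes (unfavorable", and, after a comma, a decline of more than 30%. Section 10 repeats both as conversion to "favorable, and declines by $>30" per cent. Section 12 says that CTC enumeration "will be used as a secondary marker for efficacy of response to the treatment", and Section 1.4 names CTC declines among the supportive evidence of efficacy.

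No section sets a minimum baseline count for the decline, says how a baseline of zero is handled, names the draw that is scored, or asks for confirmation. Eligibility has no CTC requirement. Other secondary endpoints are better bounded: Section 11 limits pain response to patients with a baseline PPI score of at least 2 or a need for analgesics, and limits RECIST response to measurable disease. The PSA decline has a three-month window.

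Two related passages do not agree with the rest:

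- **Cutoff.** Section 1.1 classes fewer than 5 cells per 7.5 mL as favorable and 5 or more as unfavorable. Section 10, as its text reads, prints unfavorable as 5 or fewer.
- **Draws.** Section 6.3 has "serial CTC enumeration (repeated on day 1 cycle 2, then q 3 cycles", and Section 3.1 says the same. Section 12 has "Baseline CTC will be obtained prior to initiation of therapy and day 1 of cycles 2 and 4", which agrees with the synopsis, the study calendar and Section 10.

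**The concern.** CTC is a small whole-number count from a single tube. At low counts a percentage rule is very coarse: one cell to none is a 100% decline, and three cells to two is 33%. Patients with one to four cells are already favorable by the Section 1.1 cutoff. They cannot contribute to the conversion outcome, yet they can be scored as responders on the decline outcome through ordinary counting variation.

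The trial has one arm, so no control group shows how often such declines occur without drug activity. A rate produced largely by counting noise could be read as supportive evidence for carfilzomib. Because the scored draw is not named and the schedules conflict, the number and timing of chances to meet the criterion also depend on which section a site follows.

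**Working it through.** **The plan's own figures.** The documents give no expected rate, power or precision for the CTC outcome. The only design calculation is for the primary endpoint, and it reproduces: with 25 patients and rejection at 6 or more, the exact one-sided error at 10% is 0.033 and the power at 30% is 0.807; 25 / 0.9 = 27.8, rounded up to 28. CTC plays no part in it.

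**Step 1: cells that must be lost.** For baseline b, take the smallest whole k with k / b > 0.30:

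- b = 1: lose 1 (100%)
- b = 2: lose 1 (50%)
- b = 3: lose 1 (33.3%)
- b = 4: lose 2 (50%; losing 1 is only 25%)

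This step is exact and needs no assumption.

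**Step 2: noise when the true mean equals the observed baseline.** Assume F ~ Poisson(b) with no true change. The one-draw probability is p = P(F ≤ f), where f is the largest follow-up count that is a decline of more than 30%. If either of two draws counted, it would be 1 − (1 − p)².

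| b | f | one draw | either of two |
|---|---|---|---|
| 1 | 0 | 36.8% | 60.0% |
| 2 | 1 | 40.6% | 64.7% |
| 3 | 2 | 42.3% | 66.7% |
| 4 | 2 | 23.8% | 42.0% |
| 5 | 3 | 26.5% | 46.0% |
| 10 | 6 | 13.0% | 24.3% |
| 20 | 13 | 6.6% | 12.8% |
| 50 | 34 | 1.1% | 2.1% |

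**Step 3: noise in the baseline as well, over a mixed cohort.** The documents give no CTC distribution for this trial. Section 1.1 reports "Patients with Unfavorable pretreatment CTC (57%) had shorter OS" in the cited chemotherapy cohort, so 100 − 57 = 43% of that cohort had 0–4 cells. Patient means were assumed lognormal, with log-SD from 1.0 to 2.5 and the median set so that 57% have a baseline of 5 or more. Baseline and both follow-up counts were drawn as Poisson around the same mean. A baseline of zero was scored as non-response.

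| log-SD | share with 1–4 cells | 1–4 cells: one / either draw | 5 or more: one / either draw | all patients: one / either draw |
|---|---|---|---|---|
| 1.0 | 36.7% | 30.0% / 45.6% | 27.3% / 41.4% | 26.6% / 40.4% |
| 1.5 | 32.3% | 35.4% / 51.9% | 21.1% / 32.3% | 23.5% / 35.2% |
| 2.0 | 28.1% | 38.8% / 55.5% | 17.0% / 26.1% | 20.6% / 30.5% |
| 2.5 | 24.7% | 41.0% / 57.7% | 14.0% / 21.6% | 18.1% / 26.6% |

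**Step 4: share of the cohort from the low-count group.** Multiply the share with 1–4 cells by that group's rate.

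- One draw: 0.367 × 0.300 = 11.0%; 0.323 × 0.354 = 11.4%; 0.281 × 0.388 = 10.9%; 0.247 × 0.410 = 10.1%. About 10–11%.
- Either draw: 0.367 × 0.456 = 16.7%; 0.323 × 0.519 = 16.8%; 0.281 × 0.555 = 15.6%; 0.247 × 0.577 = 14.3%. About 14–17%.

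Across all 28 patients, 18.1–26.6% is about 5 to 7 at one draw, and 26.6–40.4% is about 7 to 11 on either draw.

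**The case against.** The strongest reply is that little depends on this outcome. It is one of several secondary endpoints and has no hypothesis, threshold or decision attached. Section 1.1 already says that CTC changes need validation with biologic agents, and conversion is reported beside it. All of this stands, and it limits the point to the interpretation of supportive evidence.

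The size also rests on borrowed inputs. The 57% comes from a different cohort, and the documents give no distribution or assay variability for this one. That stands too, which is why ranges are shown. Poisson variation is close to a minimum; assay or biological variation would generally raise the rates.

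The two criteria could be read as one joint requirement, in which case an unfavorable baseline would act as a floor. The objectives list them as separate items, and no text joins them.

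Four stronger readings are tempting, and the documents do not support them:

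- A reader might put false responders from the low-count group alone at 18–30% of the cohort, by multiplying 40% by 44% to 75%. Those rates (Poisson means of 2 at one draw and 1 at either draw) are conditional on a baseline of at least one cell, whereas the group below 5 includes zeros. Without the conditioning, means of 1, 2 and 4 give 32–38% at one draw and 47–54% on either, so 0.4 times these is 13–22%. Even that includes patients whose observed baseline was 5 or more. Step 4 gives 10–11%, or 14–17%.
- A reader might take the either-draw rates as the plan's own. The plan states no such rule.
- A reader might treat 5 cells as the limit below which the assay is unreliable. Section 1.1 presents it as a prognostic cutoff, and no section describes it as an assay limit.
- A reader might conclude that the noise is confined to low counts. Step 2 gives 26.5% at a baseline of 5 and 13.0% at 10.

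**Conclusion.** The omission is real, and the cell arithmetic is exact: as written, the criterion scores the loss of one cell from one to three, or of two from four, as activity. Under the stated assumptions, noise alone produces this in about 30–41% of patients with one to four cells at one draw, or 46–58% if either of two draws counted. That is about 10–11% of the cohort from this group (14–17% on either draw), and about 18–27% across all patients (27–40%).

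These sizes depend on Poisson counts, no true change, the borrowed 57% and the assumed spread of patient means. A reader might infer that the trial's conclusion is at risk, but the primary test of 6-month PFS does not use CTC and is unaffected. This is an inexpensive improvement to a secondary endpoint.

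**What to change.** In Section 10, with matching text in the synopsis and Section 2.2:

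1. Restrict the decline outcome to patients with a baseline of at least 5 cells per 7.5 mL, the cutoff in Section 1.1.
2. Correct the unfavorable cutoff printed in Section 10 so that it agrees with Section 1.1. Otherwise the floor could be applied in the wrong direction.
3. Report patients with a baseline of 0–4 descriptively. This also settles the baseline of zero.
4. Report the rate separately at each scheduled draw, with the number sampled, and not as the best of any draw. Scoring a single draw with missing as failure is an alternative, but it is a preference and would tie the outcome to remaining on study.
5. Reconcile the draw schedule in Sections 3.1 and 6.3 with that in the synopsis, the calendar and Sections 10 and 12.

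The change is to wording only, and the floor and reporting rules need no extra sample. The denominator falls to about 0.57 × 28 = 16 patients if the borrowed share applies, and the reported rate will probably be lower. The floor is a partial remedy: at a baseline of 5 or more, noise still gives about 14–27% at one draw (22–41% on either). The plan should say so and call the rate supportive only.
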